**6.2 Statistical Methods**

**6.2.1 Accuracy will be reported as the ARMS using the following equation:**

$$Bias = \frac{1}{n} \sum_{i=1}^n (SpHb - tHb)$$

$$\text{Precision} = \sqrt{\frac{\sum_{i=1}^n ((SpHb - tHb) - Bias)^2}{n}}$$

$$A_{RMS} = \sqrt{\frac{\sum_{i=1}^n (SpHb - tHb)^2}{n}}$$

### 6.3 Additional Analyses, as applicable

#### 6.3.1 Bland-Altman bias plot

6.3.1.1 Bland Altman plots will be provided by site, by subject, and for all data combined.

6.3.1.2 A correction for repeated measures on the same subject and multiple subjects at each site will be applied during the analysis.

6.3.1.3 The limits of agreement will be calculated using the corrected variance components.

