#### 6.1.3 Effect Size

It is desired to determine if the slope of the Test on Reference regression is significantly different than [REDACTED]. All regression lines will pass through the mean point. Therefore, the slope and intercept terms are not independent and it is only necessary to check if the slope is significantly different than [REDACTED]. The levels of significance were set at [REDACTED]

[REDACTED]

For a slope range between [REDACTED], and a mean data point of [REDACTED] the intercept term will be between - [REDACTED]. Additional input constants used in the calculations are shown in Table 1 for both the Deming Slope and Deming Intercept.

Additional input constants used in the calculations are shown in Table 1 for both the Deming Slope and Deming Intercept.

██████████	██████
██████	██████
██████████	██████
██████████	██████
██████████████████	██████
██████████████████	██████
██████████████████	██████
██████████████████	██████

██████████

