#### 6.3.2 Regression Analysis

6.3.2.1 Data will be randomly resampled to provide a uniform distribution of data points across the measurement range.

6.3.2.2 To account for variation in the reference tHb values, Deming linear regression analysis will be calculated.

6.3.2.3 Estimates of standard deviation in both the SpHb and tHb data (required by Deming regression) will be calculated from earlier studies [REDACTED]

6.3.2.4 Estimates and 95% confidence intervals for both Y-intercept and Slope will be calculated for a Deming regression across all [REDACTED] sites and within each site individually.

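### Limits of agreement in 6.3.1.3 carry no hemoglobin-level term, so any slope departure would be absorbed as random variance and the limits would be off-centre at the ends of the range

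*Combined protocol and SAP*

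**What the plan says.** Section 6.3.1 has three items and no visible redaction.

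- 6.3.1.1: "Bland Altman plots will be provided by site, by subject, and for all data combined". None of these displays is split by hemoglobin.
- 6.3.1.2: "A correction for repeated measures on the same subject and multiple subjects at each site will be applied during the analysis". Subject and site are the only structures named.
- 6.3.1.3: "The limits of agreement will be calculated using the corrected variance components".

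The parent section, 6.3, is headed "Additional Analyses, as applicable". The endpoint in 4.2 and 6.2.1 is ARMS.

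The sample size rests on a different quantity. Section 6.1.3 states: "It is desired to determine if the slope of the Test on Reference regression is significantly different than", after which the value is blacked out. The slope range, mean data point and significance levels are redacted too. Section 6.3.2 then plans a Deming regression on data resampled to be uniform over the measurement range, with slope and intercept and their 95% confidence intervals, overall and by site.

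**The concern.** Limits of agreement tell a user how far one SpHb reading may lie from the laboratory value. A single bias and a single SD do this at every hemoglobin level only if the difference SpHb-tHb has no trend with level. A slope other than 1 is exactly such a trend, and the slope is what the plan chose to size the trial on.

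A model with only subject and site components has nowhere to put the trend except in those components. The SD is inflated, so the limits are too wide in mid-range. They are centred on the overall bias, so they are displaced at both ends. If SpHb compresses the range, the limits understate over-reading at low hemoglobin and under-reading at high hemoglobin. Low hemoglobin matters here, because section 1.1 presents the measurement as a help in assessing anemia. The report could show a slope below 1 beside limits that take no account of it.

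**Working it through.** **No figure to reproduce.** The documents state no limits of agreement and no coverage. The slope range, mean point, variances and resulting sample sizes are redacted, so the check below uses assumed inputs.

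**Assumptions.** Null slope 1; mean Hb μ 12-13 g/dL; SD of Hb (SDx) 1.8-2.0; residual SD (s, everything left after the trend) 0.8-1.0; zero bias at the mean; constant s; reference error ignored. Hb 8 is chosen as a low evaluation point; it does not come from the documents.

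**Model.** For true slope b, D = SpHb-tHb = (b-1)(Hb-μ) + e, with e ~ N(0, s²).

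- Pooled half-width: L = 1.96 × √(s² + (b-1)² SDx²).
- Mean difference at level h: m = (b-1)(h-μ).
- Coverage at h: Φ((L-m)/s) - Φ((-L-m)/s).
- Check: b = 1 gives 95.0%.

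**Worked case: b = 0.8, μ = 13, SDx = 2.0, s = 1.0.**

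- SD of D = √(1.00 + 0.04 × 4.00) = √1.16 = 1.077, so L = 2.11.
- At Hb 8, m = (-0.2)(-5) = +1.0.
- Share above the upper limit: 1 - Φ((2.11 - 1.0)/1.0) = 1 - Φ(1.11) = 13.3%.
- Share below the lower limit: Φ(-3.11) = 0.09%.
- Coverage: 86.6%, with the misses almost all over-readings.
- On the SpHb scale, readings at Hb 8 centre on 9.0 with a 95% range of about 7.0-11.0. The pooled limits imply 8 ± 2.11, or 5.9-10.1.

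**Over the assumed ranges:**

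| Slope | Hb 8 | At the mean | Hb 16 |
|---|---|---|---|
| 0.80 | 81.5-90.3% | 96.3-97.2% | 87.4-93.1% |
| 0.90 | 91.3-93.7% | 95.4-95.7% | 92.8-94.5% |
| 0.95 | 94.0-94.7% | 95.1-95.2% | 94.4-94.9% |

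**Sensitivity at Hb 8.** Over a wider grid (slope 0.80-0.95, μ 12-14, SDx 1.5-2.5, s 0.8-1.2) coverage runs from 72% to 95%. With Hb uniform on 8-17 (mean 12.5) and s 0.8-1.2 it is 88.7-91.5% at slope 0.8 and 92.9-94.0% at slope 0.9.

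**Simulation with clustering.** Four sites × 60 subjects × 2 readings, Hb N(13, 2.0), subject SD 0.9, within-subject SD 0.45, slope 0.8. The estimated between-subject variance rises from 0.81 to 0.97. The increase of 0.16 equals (b-1)² SDx² = 0.04 × 4, so the trend is indeed absorbed as between-subject variance. Coverage at Hb 8/10/13/16 is 86.5/93.0/96.4/93.0% with pooled limits and 94.6/94.8/94.9/94.8% with limits around a line fitted on Hb.

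**Choice of level variable.** Take slope 1, SpHb error SD 1.0, reference error SD 0.3 and Hb SD 1.8 (variances 1.00, 0.09, 3.24).

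- Difference regressed on tHb: -0.09/(3.24 + 0.09) = -0.03 per g/dL.
- Difference regressed on the average of the two methods: ((1.00 - 0.09)/2)/(3.24 + (1.00 + 0.09)/4) = 0.455/3.5125 = +0.13 per g/dL.

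The average would create a visible trend where none exists; tHb nearly does not.

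**The case against.** **The size rests on a slope the plan does not disclose.** A reader might infer that the trial is sized to detect 0.8, and that 82-90% coverage therefore follows from its own target. The documents do not support this, because the slope range is redacted. A rough calculation even leans towards a smaller departure. With n = (1.96 + 0.84)² s²/(δ² SDx²), the assumed SDs give about 31-61 subjects for δ = 0.2 and 126-242 for δ = 0.1, before site inflation, against an enrolment ceiling of 300 (section 4.5). The inflation factor is redacted, so this settles nothing, but 0.9 fits at least as well as 0.8. This part of the objection stands.

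**Hb 8 is an extreme.** Under the assumed normal distributions only 0.3-2.3% of subjects, about 1-7 of 300, would be at or below 8. If enrolment spreads hemoglobin out, the shortfall is milder, as the uniform case shows. This also stands. It limits the size of the effect, and it limits the precision of level-specific limits there.

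**The trend is already analysed.** The Deming slope and intercept would reveal a proportional bias, and the Bland-Altman plots would show it by eye. That is right: the plan would not miss the trend. But slope and intercept do not say how far an individual reading may lie from the reference at a given level, and no item links 6.3.2 to 6.3.1.3.

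**Pooled limits are correct on average, and the analysis is additional.** Both are true. No visible acceptance criterion uses the limits. However, section 6.1.5 lets patient availability set the numbers per site, so the mix being averaged over is partly incidental, and a spot-check reading is read for one patient.

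**One constant pair of limits.** A reader might say the plan prescribes this. It does not say so: plots are made by site and by subject as well as combined, and the absence of a level term is inferred from silence. The supportable statement is that none of the described limits varies with hemoglobin.

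**Conclusion.** The concern holds in a limited form. As written, 6.3.1.3 would fold any slope departure into the variance components. The limits would be right on average over the enrolled mix, too wide mid-range and off-centre at the ends.

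The size depends on redacted inputs. Under the assumptions above, the loss at Hb 8 is about 5-13 percentage points at slope 0.8, 1-4 at slope 0.9 and 1 or less at slope 0.95. If the slope is close to 1, there is practically no problem. None of these figures is a property of the plan.

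The direction does not depend on the exact inputs: with any slope below 1, the excess misses at low hemoglobin are over-readings. This is worth correcting because the slope is the plan's own sizing question. It is an improvement to an additional analysis and does not touch the ARMS endpoint.

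**What to change.** Add to 6.3.1.3:

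> SpHb-tHb will also be modelled as a linear function of tHb with the same subject and site random effects. Bias and 95% limits from this model will be drawn, and tabulated at fixed tHb levels within the observed range, beside the pooled limits, in all cases and without a preliminary test.

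Name tHb as the single level variable, and note the small tilt from reference error (about -0.03 per g/dL under the SDs assumed above).

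**Cost.** One addition to the plan and one more table and plot from data already collected; no extra subjects or procedures.

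**Downside.** The level-specific limits assume a linear trend and a constant residual SD, and are less precise where few subjects are enrolled, which may include the low end. Showing both sets lets the reader judge. If the slope is near 1 they will nearly agree.

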#### 6.3.2 Regression Analysis

6.3.2.1 Data will be randomly resampled to provide a uniform distribution of data points across the measurement range.

6.3.2.2 To account for variation in the reference tHb values, Deming linear regression analysis will be calculated.

6.3.2.3 Estimates of standard deviation in both the SpHb and tHb data (required by Deming regression) will be calculated from earlier studies [REDACTED]

6.3.2.4 Estimates and 95% confidence intervals for both Y-intercept and Slope will be calculated for a Deming regression across all [REDACTED] sites and within each site individually.

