#### 4.5 Number of Subjects

There will be up to 300 subjects enrolled into this study. The anticipated duration of subject participation in this study will be approximately 1-2 hours in the clinic and up to 72 hours from the time subject leaves the clinic, if subject receives an arterial blood draw. The study enrollment period is expected to be approximately 3 months.

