**6.1.4 Monte Carlo Simulation**

The data from the earlier study contained data from ██████████. This data was resampled by Subject (with replacement) to simulate data sets with differing numbers of Subjects.

A Deming regression was calculated for each of ██████ iterations. The Slope and Intercept from each regression were stored and the statistics required to meet the effect size requirements were calculated for each level of subjects. These simulations indicated that the Slope effect size of ████████████████████. Similarly, ██████████ would be required to meet the Intercept requirement. The initial sample size, assuming the measurements are all independent, is set to ██████████

The initial sample size, assuming the measurements are all independent, is therefore set to ██████████

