**6.1.5 Intraclass Correlation Coefficient**

Since this protocol will be run in several clinical sites, an evaluation of the Intraclass Correlationiii was performed. Based on the Site to site variation seen in the earlier study, the Between Site variance component was ██████. The Across Site variance was calculated as ██████. The ICC is found by:

$$ICC = \frac{AcrossSiteVariance}{AcrossSiteVariance + BetweenSiteVariance} = ██████$$

This gives a Sample Size Inflation factor of:

$$██████████████████$$

Therefore, this study will use a minimum of ██████████ total subjects. Additional subjects may be required to fill in demographic bins or account for subject drop out of ██████

In order to collect data across multiple subject health conditions, █ sites will be utilized. The number of subjects per site will be determined by patient availability and patient demographics at each site. This will ensure that other study endpoints related to the distribution of observed hemoglobin values are also met.

Final statistical analysis will be performed on a population set who have enrolled and completed the study procedure as defined per the protocol.

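### Section 6.3.2.1 puts a random draw before the Deming fit: unless many draws are averaged, the slope depends on the draw, and under linearity one draw gives poorer inference than fitting all pairs

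*Combined protocol and SAP*

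**What the plan says.** Section 6.3.2.1 reads: "Data will be randomly resampled to provide a uniform distribution of data points across the measurement range". A Deming fit follows (6.3.2.2), using error SDs from earlier studies (6.3.2.3). Section 6.3.2.4 then asks for "Estimates and 95% confidence intervals for both Y-intercept and Slope will be calculated for a Deming regression across all" the (redacted number of) "sites and within each site individually".

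The readable text of 6.3.2 does not give the unit drawn, whether drawing is with replacement, the size or number of draws, or an interval method that allows for the draw. The opening of section 6, most of 6.4, and parts of 6.1 and 6.3.2.3 are redacted, so such a rule may exist there.

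The planning simulation in 6.1.4 does name its unit and rule: "This data was resampled by Subject (with replacement) to simulate data sets with differing numbers of Subjects". That is a different step, applied to earlier-study data.

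Section 6.3.1.2 states that "A correction for repeated measures on the same subject and multiple subjects at each site will be applied during the analysis"; in the readable text this appears only under Bland-Altman. The regression sits under the 6.3 heading, "Additional Analyses, as applicable". The endpoint in 4.2 and 6.2 is A_RMS.

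**The concern.** A random draw placed between the data and the fit adds noise that the study did not collect. If rows are copied, an ordinary interval counts the copies as new subjects and comes out too short. If rows are dropped, information is lost. Either way another seed gives another slope from the same data, and by-site fits, with fewer subjects, move more.

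The regression is not the endpoint, but it matters: the readable sample-size text (6.1.3, 6.1.4) is built on the Deming slope and intercept. A reader will look to these intervals to judge whether the device tracks the reference across the Hb range.

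**Working it through.** **No plan figure to reproduce.** The slope limits, significance levels, variances and required N are redacted.

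**Inputs.** From the documents: Deming regression, 95% intervals, and the enrolment ceiling ("There will be up to 300 subjects enrolled into this study"). Assumed, because the documents do not give them:
- Set A: Hb 8-17 g/dL, error SDs 0.3 (reference) and 0.9 (device), 1 g/dL bins on tHb.
- Set B: Hb 7-18 g/dL, error SDs 0.2 and 1.0, 1 g/dL bins.
- Both: true line y = x, one pair per subject, n=300, bell-shaped Hb with mean 13 unless stated.

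**Estimator.** With d = (device SD / reference SD)², slope b = [Syy − d·Sxx + √((Syy − d·Sxx)² + 4d·Sxy²)] / (2·Sxy). Set A has d = (0.9/0.3)² = 9; set B has d = (1.0/0.2)² = 25. Intervals use a jackknife SE.

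**Step 1: closed form for uniform Hb.** Let the all-pairs slope have variance V. A same-size draw with replacement adds about V more, so the total is 2V, while the ordinary interval still uses V. Coverage = 2Φ(1.96/√2) − 1 = 2Φ(1.386) − 1 = 83.4%. No assumed SD enters. In set B with nearly flat Hb, the empirical SD was 0.0263 against a mean SE of 0.0185 (ratio 1.42, close to √2), and coverage was 83.8%.

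**Step 2: simulation, set A.** All pairs cover 95% throughout.

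| Hb distribution | With replacement, ordinary CI: coverage | Without replacement: pairs kept | CI width vs all pairs |
|---|---|---|---|
| Bell-shaped, SD 1.8 | 53% | 9% | 2.1 |
| Bell-shaped, SD 2.2 | 66% | 21% | 1.6 |
| Half-enriched (intermediate) | 79% | 51% | 1.2 |
| Uniform | 83% | 75% | 1.15 |

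With 3 g/dL bins the effects shrink: 75% (SD 1.8) to 84% (uniform) coverage with replacement, and 1.26 to 1.04 times the width without.

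**Step 3: set B, SD 1.8.** All pairs 95.2%; with replacement 46.6%; without replacement 94.2%, with about 31 pairs kept and 1.99 times the width. The direction matches set A.

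**Step 4: dependence on the draw.** In set A, redraws of one fixed data set put 95% of slopes within a span of 0.072-0.077. The all-pairs interval is 0.129 wide (SD 1.8) or 0.084 (uniform), so the span is 56-60% or 86-92% of that width. In set B the SD over redraws is 0.019, giving 2 × 1.96 × 0.019 = 0.074. It rises to 0.027 at n=150 and 0.041 at n=75, sizes closer to a by-site fit.

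**Step 5: the draw-free alternative.** The mean of many redraws differed from an inverse-bin-count weighted fit by 0.001 or less. Averaging therefore reproduces fixed weights. Full uniform weights in set B and its variants (bins on measured tHb) gave intervals 1.01 to 1.84 times the all-pairs width, with coverage 87-94%. Bins on measured tHb also pull the slope down slightly (set A mean 0.979 at SD 1.8, 1.000 if uniform). Bins on the Deming-fitted value with sparse bins merged gave a mean of 1.000 at SD 1.8; coverage was 95-98% and width 1.02-1.22 times over the cases run.

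**The case against.** The strongest reply is that only one reading gives a consistently short interval, namely rows copied with replacement and an ordinary interval, and the plan does not state that reading. Without replacement, coverage holds. Bootstrapping the whole procedure by subject covered 89% (SD 1.8), 97% (half-enriched) and 98.5% (uniform). Averaging many draws, which redacted text may prescribe, removes the dependence on the draw. This stands: the low coverage figures describe one possible implementation, not the plan's known behaviour.

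Second, much of the extra width is the price of uniform emphasis, not of randomness, and fixed weights share it. This also stands.

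Third, uniform emphasis has a purpose. With assumed curvature of 0.02 or 0.04 per (g/dL)² about 12.5, the all-pairs slope is 1.015 or 1.029 at mean Hb 13, and 1.040 or 1.086 at mean 14, against 1.000-1.005 with uniform weights. That supports weighting, but it does not require a random draw.

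Fourth, 6.1.5 says of subject numbers per site: "This will ensure that other study endpoints related to the distribution of observed hemoglobin values are also met". Recruitment may therefore be near uniform, where the effects are smallest.

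A reader might also infer that the study was sized for a more precise slope than 6.3.2.1 will deliver, or that two analysts must obtain different results. The documents support neither. The required N, the effect size and the earlier study's Hb distribution are redacted, and a seed or averaging rule may be as well.

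**Conclusion.** The concern holds in a limited form. As readable, 6.3.2.1 makes the slope depend on a random draw unless many draws are averaged. If SpHb is linear in tHb, a single draw is worse than using all pairs. With replacement and an ordinary interval, coverage is too low: 83% in closed form for uniform Hb, and about 53% in the bell-shaped case of set A. Without replacement the interval is about 1.15 to 2.1 times wider with 1 g/dL bins.

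The direction held under both sets of assumptions. Apart from the closed-form result, the sizes depend on assumed Hb spread, error SDs and bins. It should not be read as a defect in the endpoint: A_RMS is unaffected, the regression is an additional analysis, and no readable success criterion rests on its interval. It is worth correcting because the readable sample-size text rests on the same slope and intercept.

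**What to change.** - Make the Deming fit to all evaluable pairs the reported regression, pooled and per site.
- Take slope and intercept intervals from a jackknife or bootstrap of original subjects, keeping each subject's readings together. With three assumed readings per subject (subject-level device SD 0.7, total 0.9), treating rows as independent covered only 80% even with all pairs. The subject jackknife covered 95-96%.
- If equal influence across the Hb range is wanted, report beside it a fit with prespecified inverse-bin-count weights and no random draw. Form the bins on the Deming-fitted value rather than measured tHb, and recompute the weights in each replicate.
- If sparse bins are to be merged, prespecify the minimum count. The checks used 10 subjects per bin pooled and 5 per site.
- If a resampling rule exists in redacted text, cite it from 6.3.2.1 and still report the all-pairs fit.

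**Cost.** SAP wording and a few lines of code, with no new data. The weighted interval is wider than the all-pairs one, about 1.0 to 1.8 times with full uniform weights depending on Hb spread. Merging narrows it to 1.02-1.22 times but gives up part of the uniform emphasis. With curvature 0.02, mean Hb 14 and n=300, the slope averaged 1.041 for all pairs, 1.019 with merged bins and 1.002 with full weights. Merging thus keeps (1.041 − 1.019)/(1.041 − 1.002) = 0.022/0.039, or 56%, of the correction.

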### **1.1 Background and Rationale**

Hemoglobin (Hb) is a protein contained in the red blood cells that is responsible for carrying oxygen from the lungs to tissues throughout the body. The concentration of hemoglobin in whole blood is expressed in grams per deciliter (g/dL). Normal Hb range for adult males is 13 to 18 g/dL and 12 to 16 g/dL for adult females. Sufficient hemoglobin level must be maintained to ensure adequate tissue oxygenation; a person with low levels of hemoglobin is referred to as anemic. Some common causes of anemia are:

- Nutritional deficiency - iron, vitamin B12 and folate
- Abnormal hemoglobin structure - sickle cell or thalassemia
- Acute loss of blood due to traumatic injury or surgical procedure
- Chronic diseases - cancer, kidney and liver failure

If left untreated, anemia can cause several complications, such as:

- Fatigue
- Heart problems, such as arrhythmia
- Death in the case of acute blood loss

To assess a patient's anemia status, a physician would typically request a complete blood count (CBC) test to evaluate hemoglobin levels. The National Committee for Clinical Standards (NCCLS) has published an approved gold standard procedure for the manual measurement of hemoglobin using the cyanmethemoglobin method (HiCN). This method breaks down red blood cells to get the hemoglobin into a solution. Then, the free hemoglobin is oxidized to form methemoglobin and combined with cyanide ions, resulting in cyanmethemoglobin. The concentration of hemoglobin is then determined by shining a light through the solution and measuring how much light is absorbed- specifically at a wavelength of 540 nanometers. Manual HiCN has gradually been phased-out of mainstream laboratory use, because it is time and labor intensive and exposes the operator to harmful reagents. Instead, there are automated analyzers based on the same operating principle of HiCN that are more widely used, such as Beckman Coulter and Advia 120, and Sysmex hematology analyzers. However, HiCN still remains that reference method that all automated analyzers are compared against.

[figure not shown]

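### The additional Deming regression gives a confidence interval for offset only at a hemoglobin of 0 g/dL; offsets at real hemoglobin levels are available from the same fit at no cost

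*Combined protocol and SAP*

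**What the plan says.** Section 6.3.2 (Regression Analysis) sits under 6.3, a set of additional analyses to be done as applicable. It plans a Deming regression of SpHb on tHb with this output: "Estimates and 95% confidence intervals for both Y-intercept and Slope will be calculated", for a fit pooled over all sites and also within each site. Before the fit, "Data will be randomly resampled to provide a uniform distribution of data points across the measurement range". The visible text does not give that range.

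The sizing sections treat slope and intercept as a pair. Section 6.1.3 states "All regression lines will pass through the mean point", derives an intercept range from the slope range, and concludes that "it is only necessary to check if the slope is significantly different than" a redacted value. Section 6.1.4 nevertheless simulates a number of subjects, redacted, that "would be required to meet the Intercept requirement".

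On plausible hemoglobin values, section 1.1 says: "Normal Hb range for adult males is 13 to 18 g/dL and 12 to 16 g/dL for adult females". Section 4.4 also admits non-healthy adults, so lower values are to be expected.

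The endpoint is A_RMS (4.2), reported with Bias and Precision (6.2.1). Bland-Altman plots and corrected limits of agreement are planned in 6.3.1.

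**The concern.** A reader of the regression output will want to know whether the device reads high or low at a hemoglobin that matters clinically, and how precisely that is known. The planned output answers this only at 0 g/dL. There, the uncertainty is almost entirely the slope's standard error multiplied by the mean hemoglobin. An intercept interval that covers 0 is therefore weak evidence that the offset is small at 10 or 13 g/dL.

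The reasoning in 6.1.3 does not close the gap. The fitted line passes through the point (mean tHb, mean SpHb), but that point need not lie on the line of identity. A device with slope 1 and a constant offset would pass a slope-only check, which leaves the intercept interval as the regression's only guard against such an offset.

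The separate slope and intercept intervals also cannot be combined into an interval at a chosen hemoglobin, because that needs their covariance, which the visible plan does not report.

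**Working it through.** The plan's own figures cannot be reproduced. The significance level, effect sizes, mean data point, variances, Table 1 and simulated subject numbers are all redacted. The check below therefore rests on assumptions.

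**Inputs**
- From 6.3.2.1: tHb is uniform over a range after resampling. The range is assumed: 6-18, 7-17 or 8-17 g/dL. Mean m = midpoint; SD s = width / sqrt(12).
- Assumed error SDs: 0.8 g/dL for SpHb and 0.2 g/dL for tHb. Assumed N = 150 independent points (4.5 caps enrollment at 300; the effective number after resampling is unknown).
- Assumed true slope 1 and constant offset 0.5 g/dL.

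**Formulas**
- Error variance v = 0.8^2 + 0.2^2 = 0.68.
- SE(slope) = sqrt(v/N) / s.
- SE of fitted offset at level h = sqrt(v/N + (h - m)^2 x SE(slope)^2). The intercept is h = 0.
- Detection = P(95% interval excludes 0), approximately Phi(0.5/SE - 1.96).

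**Worked case, 8-17 g/dL**
- m = 12.5; s = 9/sqrt(12) = 2.598; v/N = 0.68/150 = 0.00453.
- Center: SE = 0.0673, half-width 1.96 x 0.0673 = 0.13 g/dL.
- SE(slope) = 0.0673/2.598 = 0.0259.
- Intercept: SE = sqrt(0.00453 + 12.5^2 x 0.0259^2) = 0.331, half-width 0.65. Detection = Phi(1.51 - 1.96) = 33%.
- End (8 or 17): SE = sqrt(0.00453 + 4.5^2 x 0.0259^2) = 0.135, half-width 0.26. Detection = Phi(3.71 - 1.96) = 96%.

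**All three ranges, N = 150**

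| Range (g/dL) | Half-width: intercept / end / center | Width ratio to center / to end | Detection: intercept / end / center |
|---|---|---|---|
| 6-18 | 0.48 / 0.26 / 0.13 | 3.6 / 1.8 | 54% / 96% / about 100% |
| 7-17 | 0.56 / 0.26 / 0.13 | 4.3 / 2.1 | 41% / 96% / about 100% |
| 8-17 | 0.65 / 0.26 / 0.13 | 4.9 / 2.5 | 33% / 96% / about 100% |

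The end value is the same in every row because, for a uniform range, the ends lie sqrt(3) SDs from the mean, so the half-width there is always twice that at the center. Simulated Deming fits under the same assumptions (10,000 per range) gave intercept detection of 32-52% and 96% at the ends, in line with the formula.

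**Sensitivity**
- Narrower ranges: ratios of 6.3 (center) and 3.1 (end) for 9-16 g/dL, and 8.7 and 4.4 for 12-18 g/dL.
- N = 300: intercept detection 57-83% over the three ranges.
- One site, assumed n = 50: intercept detection 14-22%; at the ends SE = 2 x sqrt(0.68/50) = 0.233, detection 57%; at the center 99%.
- A separate simulation with SDs 0.9 and 0.3, n = 200, range 8-17 and a 0.3 g/dL offset: 15% from the intercept, 60% at 8 g/dL, 99% at 12.5 g/dL.

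**Overlap with the slope.** Correlation of intercept and slope = -m / sqrt(m^2 + s^2): -0.96 for 6-18 and -0.98 for 8-17.

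**Why the covariance matters.** Var(offset at h) = Var(intercept) + h^2 Var(slope) + 2h Cov. At 12.5 g/dL in the worked case, leaving out the covariance gives SE = sqrt(0.331^2 + 12.5^2 x 0.0259^2) = 0.463 and a half-width of 0.91 instead of 0.13 g/dL.

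**The case against.** The strongest objection is that a constant offset is exactly what Bias measures. Bias is reported with the endpoint. With the SDs of 0.8 and 0.2 g/dL and N = 150, its half-width would be 0.13 g/dL, the same as the fitted offset at the center. A_RMS absorbs any offset, and Bland-Altman plots would display differences against level. This stands. A reader might infer that the trial as a whole would miss such an error, and the documents do not support that. What remains is narrower: these are overall summaries or plots, the visible text attaches no confidence interval to Bias, and none states the offset with its uncertainty at a low or high hemoglobin.

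Two further objections also stand. The regression is an additional analysis, and no visible decision rule uses the intercept interval. The slope and intercept estimates do fix the fitted line, so the point estimate at any hemoglobin follows from them; only its interval is missing.

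A reader might also infer that 6.1.4 sizes the study on the wrong quantity. That cannot be shown. The slope is sized too, 6.1.3 says that only the slope needs checking, and the redactions hide which requirement set the number. If the intercept tolerance is taken as mean x (1 - slope), the intercept needs only about 1-8% more subjects than the slope for ranges from 12-18 to 6-18 g/dL.

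**Conclusion.** The point holds as a gap in the reported regression output. The only offset given an interval is at 0 g/dL, outside the data. Under assumed uniform ranges of 6-18 to 8-17 g/dL, that interval is about 3.6 to 4.9 times as wide as at the center and 1.8 to 2.5 times as wide at the ends. Its chance of showing a 0.5 g/dL constant offset at N = 150 is about 33-54%, against about 96% or more inside the range. Per-site fits are weaker still.

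Two stronger readings are not supported. It is not true that the intercept cannot detect an offset: 33-54% is poor but not nil, and it rises with N. Nor is the interval several times wider at every real hemoglobin: at the ends of a range that includes anemia the factor is about 2.

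The sizes depend on the assumed range, error SDs, independence and N after resampling. The width ratios depend only on the distribution of tHb. Only a constant offset was examined for detection; an error that changes with level would also move the slope. The endpoint is unaffected.

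**What to change.** In 6.3.2.4, keep the Deming fit and add predicted SpHb minus tHb (intercept + slope x h - h) with a 95% confidence interval at hemoglobin levels fixed before the data are seen: 12 and 13 g/dL, the lower normal limits in 1.1, plus one level near each end of the measurement range. Report these pooled and by site. Compute the interval with the intercept-slope covariance, or by recomputing the offset in each jackknife or bootstrap replicate. Keep the Y-intercept as a descriptive number only.

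No change to the sample size section is asked for. The cost is one sentence in the plan and a few table rows from the same fit, with no new data. This is a free improvement.
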